| ENDPOINTS | Primary Endpoints: |
| | Total volume of voids over a 6-hour period Total natriuresis over a 6-hour period |
| | Secondary endpoints: |
| | Volume of voids between 0-2 hours, 2-4 hours and 4-6 hours post initiation of treatment. Heart Failure Symptom Scoring/Symptom Improvement- (Kansas City Cardiomyopathy questionnaire) Overall Satisfaction with Treatment- (Treatment Satisfaction |
| | Survey) |
| | Safety endpoints: |
| | Patient reported Pain Increases in serum creatinine of 0.5 mg/dL or greater Local skin reactions including hematoma, induration, infection, thrombosis, necrosis etc. Occurrence of treatment-emergent Adverse Events (AEs) or Serious Adverse Events (SAEs) |
| STATISTICAL ANALYSIS | Determination of Sample Size: For this pilot study, the determination of sample size was primarily based on clinical consideration; with the aim to yield meaningful preliminary data. |
| | Statistical Analysis Plan: A full statistical analysis plan will be developed. All data will be analyzed as intention-to-treat. Continuous variables will be presented as mean \pm standard deviation and will be compared using the Students t -test (2-tailed), unpaired. Differences between treatment groups for the categorical variables will be analyzed using the chi-square test. For the purposes of this study, P values \leq .05 will be considered significant. |
| | Early Stopping Rules: The study will be stopped early if there is a significant difference in number of patients with intolerable side effects: Ototoxicity, severe discomfort, burning and stinging at the access site, itching, and/or pain. |

| Time and Events Table | Screening Phase | Pre-Dose | Start of Dosing | Dosing | 6 hours post Start of Dosing |
|---|--------------------|----------|--------------------|--------|---------------------------------|
| Informed Consent | Х | | | | |
| Confirmation of Eligibility | Х | | | | |
| Co-morbidity | Х | | | | |
| Cardio-Pulmonary Examination | Х | | | | |
| Serum Creatinine | Х | | | | Х |
| Weight and Height | Х | | | | |
| Vital Signs | Х | Х | Х | Х | Х |
| 12-lead EKG | Х | | | | |
| Collection and Measurement of Urine Voids | | | Х | Х | Х |
| Urine Sodium | | Х | | | Х |
| Clinical Chemistry | Х | | | | Х |
| BNP/NT ProBNP | | Х | | | Х |
| Study Drug Administration | | | Х | | Х |
| Injection Site Pain Assessment | | | | | Х |
| Injection Site Inspection | | Х | | | Х |

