3. INVESTIGATIONAL PLAN

3.1. Overall Study Design and Plan

This clinical trial is a prospective, randomized, parallel-group pilot study comparing the intravenous administration of Furosemide Injection, USP, to subcutaneous administration of a buffered furosemide formulation – Furosemide Injection Solution (SCP-101), in patients presenting to the Johns Hopkins Hospital Heart Failure Bridge Clinic with decompensated heart failure. Patients presenting to the HFBC will be assessed to determine whether they need IV diuretics. If they need it, they will be screened for eligibility. If they are eligible, written informed consent will be provided. Patients will then be randomized to receive Furosemide Injection, USP intravenously, or SCP-101 delivered subcutaneously. The IV patients will get the usual care of the Heart Failure Bridge Clinic, which includes having an IV placed and delivery of a one-time dose of IV furosemide with the dose determined by the providers (maximum dose 160mg IV). The subcutaneous patients will receive 80mg of Furosemide Injection Solution, 8 mg/mL, administered subcutaneously over 5 hours (30mg in first hour and 12.5mg/hour for 4 hours).

Administration will take place with the BBraun Perfusor® Space Infusion Pump System and a standard commercial infusion set. Both groups of patients will be observed for 6 hours to assess diuresis. The goal will be to enroll a total of 40 patients, 20 in the IV furosemide group, and another 20 in the subcutaneous furosemide group. Vital signs and urine output

will be monitored closely for 6 hours. Patients will be asked to fill out a survey about their symptom improvement (Kansas City Cardiomyopathy questionnaire) and overall satisfaction related to the treatment experience. They will also be monitored for side effects including ototoxicity and discomfort at the access site (burning, itching, and pain). Electrolytes and renal function will be checked once after the patients receive diuretic therapy. Study participants will be on fluid restriction during the study, with no more than 100 ml of fluid consumed during the 6 hours.

Study Drug:

- *Furosemide Injection, USP:* Furosemide Injection, Solution, single dose determined by Investigator (maximum dose 160mg) administered intravenously by IV bolus over approximately 2 minutes (reference treatment).

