3.1.1. Endpoints

Primary Endpoints:

- 1) Total volume of voids over a 6-hour period
- 2) Total natriuresis over a 6-hour period

Secondary endpoints:

- 1) Volume of voids between 0-2 hours, 2-4 hours and 4-6 hours post initiation of treatment.
- 2) Heart Failure Symptom Scoring/Symptom Improvement- (Kansas City Cardiomyopathy questionnaire)
- 3) Overall Satisfaction with Treatment- (Treatment Satisfaction Survey)

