5.6. Prior and Concomitant Therapy

Heart failure patients are generally on multiple medications used in the management of heart failure. Additionally the majority of patients are on prescription or over-the-counter medications for one or more co-morbidities. The clinic staff will evaluate these medications on a case by case basis and decide what medications may be used on the day of administration. This determination will be made prior to randomization.

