6. STUDY PROCEDURES

6.1. Study Measurements and Assessments

6.1.1. Assessment of Efficacy

Diuresis:

Urine will be collected from start of treatment through 6 hours post initiation of treatment. Individual voids will be measured and then pooled over the 6 hour time period, and the volume of the pool will be recorded. Time of voids and volume of each void will be recorded.

Natriuresis:

Participants will not be given any fluid by mouth during the 6-hour observation period, except when required for taking oral medication, in which case fluid intake will be limited to 100mL over the 6 hour period.

A 5mL aliquot of the first void, and a 5 mL aliquot of the total 6 hour pool will be obtained by the study staff for determination of sodium.

Symptomatic Improvement

Symptom scoring using the Kansas City Cardiomyopathy questionnaire will be performed prior to drug administration and at the end of the 6 hour observation period. A treatment satisfaction survey will be conducted at 6 hours.

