8.2. Statistical Analysis Plan

A full statistical analysis plan will be developed. All data will be analyzed as intention-totreat. Continuous variables will be presented as mean \pm standard deviation and will be compared using the Students *t*-test (2-tailed), unpaired. Differences between treatment groups for the categorical variables will be analyzed using the chi-square test. For the purposes of this study, *P* values $\leq .05$ will be considered significant.

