8.3. Safety Analyses

Extent of Exposure, Adverse Events, Clinical Laboratory Assessments and Vital Signs will be summarized with descriptive statistics.

Pain assessments and local injection site reactions will be tabulated and assessed using descriptive statistical analysis.

9. **RESPONSIBILITIES**

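### KCCQ is scored before dosing and at 6 h, but the planned unpaired t-test ignores the pre-dose score and does not say which KCCQ quantity is compared: a minor, nearly free gain in precision

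*Combined protocol and SAP*

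**What the plan says.** Section 3.1.1 lists as its second secondary endpoint "Heart Failure Symptom Scoring/Symptom Improvement- (Kansas City Cardiomyopathy questionnaire". Section 6.1.1 sets the timing: the "questionnaire will be performed prior to drug administration and at the end of the 6 hour observation period".

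Section 8.2 gives one between-group method for continuous variables, which are to be "compared using the Students *t*-test (2-tailed), unpaired". The synopsis repeats it ("compared using the Students t -test (2-tailed), unpaired"). Neither place names the KCCQ, a baseline covariate, or the quantity to be compared. Section 8.3 makes another set of measures descriptive: "Extent of Exposure, Adverse Events, Clinical Laboratory Assessments and Vital Signs will be summarized with descriptive statistics", followed by pain and injection-site reactions. The KCCQ is not among them, so the rule in 8.2 applies to it. That reading treats the KCCQ as continuous, which is natural but not stated.

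Section 8.2 also promises more: "A full statistical analysis plan will be developed".

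On order of events, section 3.1 moves from consent straight to allocation ("Patients will then be randomized to receive Furosemide Injection, USP intravenously"). Both time-and-events tables (the synopsis and Appendix 1) mark randomization under Screening and the first KCCQ under Pre-Dose. Section 5.5 states that the trial is open label. Section 5.6 places the decision on concomitant medication ahead of allocation ("This determination will be made prior to randomization"); no section does the same for the KCCQ.

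**The concern.** A pre-dose KCCQ will be collected on every patient, yet the stated test makes no use of it as a covariate. Two things are at stake.

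- **Precision.** With 20 per arm the interval is wide, and the pre-dose score may explain part of the spread at 6 h.
- **An open choice.** The 6 h-score estimate and the change estimate differ by exactly the chance difference between arms at baseline. If the choice stays open until the data are seen, the result can depend on it. ANCOVA removes this choice, because the adjusted treatment difference is the same whether the outcome is the 6 h score or the change.

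Both the change analysis and ANCOVA use the pre-dose score, so it matters that knowledge of the arm has not influenced that score. The documents do not secure this.

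**Working it through.** **Inputs.** From the documents: 20 per arm (section 3.1), an unpaired two-sided t-test and a 0.05 threshold (section 8.2). The plan has no KCCQ figure to reproduce: section 8.1 bases the sample size on clinical consideration, and no KCCQ SD or pre-post correlation is given. Assumed: the correlation r, and k = pre-dose SD / 6 h SD (k = 1 unless stated).

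**Half-widths of the 95% CI, in units of the 6 h SD.** sqrt(2/20) = 0.316; t on 38 df = 2.0244; t on 37 df = 2.0262.

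- 6 h score: 2.0244 × 0.316 = 0.640
- Change: 0.640 × sqrt(1 + k² − 2rk), which is 0.640 × sqrt(2(1 − r)) at k = 1
- ANCOVA: 2.0262 × 0.316 × sqrt((1 − r²) × 37/36), where 37/36 is the average cost of estimating the slope

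| r (k = 1) | 6 h score | Change | ANCOVA | ANCOVA vs better t-test |
|---|---|---|---|---|
| 0 | 0.640 | 0.905 | 0.650 | 1.5% wider |
| 0.3 | 0.640 | 0.757 | 0.620 | 3% narrower |
| 0.5 | 0.640 | 0.640 | 0.563 | 12% narrower (maximum) |
| 0.8 | 0.640 | 0.405 | 0.390 | 4% narrower |

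**Break-even at k = 1.** ANCOVA equals the 6 h-score t-test at r = 0.170 and the change t-test at r = 0.942. Between these values it is narrower than both. Simulation (40,000 trials per r) agrees: 12.2% narrower at r = 0.5, no gain at 0.17, and 0.1% at 0.94.

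**Unequal SDs, against the better t-test.**

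- k = 0.8: 4% narrower at r = 0.5 and 1.5% wider at r = 0.8. ANCOVA is wider than the change t-test for r of about 0.67 to 0.88.
- k = 0.9: wider than the change t-test for r of about 0.80 to 0.95.
- k = 1.25: 12% narrower at r = 0.5 and 19% at r = 0.8.

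**Largest possible loss.** 1 + k² − 2rk is smallest at k = r, where it equals 1 − r². The ratio of ANCOVA to change is then sqrt(37/36) × 2.0262/2.0244 = 1.015. Against the 6 h score the ratio is largest at r = 0, again 1.015. So on average ANCOVA cannot lose more than about 1.5% to either t-test, whatever r and k are.

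**The open choice.** At k = 1 the baseline difference has SE 0.316 SD, so the two t-test estimates differ by 0.32 SD or more in about 32% of trials. That is half of the 0.640 half-width. In null simulations with a sound baseline each t-test rejects about 5% of the time, but at least one of the two rejects in about 9% (r = 0.5) to 9.5% (r = 0.8).

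**If the arm is known before the pre-dose KCCQ.** Take an illustrative shift of 0.25 SD in one arm (not from the documents), with r = 0.5 to 0.8 and no true effect:

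| What is shifted | Analysis | Bias (SD) | Type I error |
|---|---|---|---|
| Pre-dose score only | 6 h score | 0 | 5% |
| | Change | −0.25 | 12–23% |
| | ANCOVA | −0.125 to −0.20 | 7–17% |
| Both scores | 6 h score | 0.25 | 12% |
| | Change | 0 | 5% |
| | ANCOVA | 0.125 to 0.05 | 7–6% |

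The ranking of the 6 h-score and change analyses reverses between the two scenarios. ANCOVA lies between them in both.

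**The case against.** The strongest reply is that nothing here is wrong. Both t-tests are valid, the endpoint is secondary, the trial is a pilot, the primary endpoints of urine volume and sodium are untouched, and section 8.2 defers detail to a fuller SAP. All of that stands and sets the weight of the point. It does not remove it: the content of that SAP is not in the documents, and a SAP cannot repair a baseline scored after the arm was known.

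Second, the endpoint's wording speaks of improvement, which leans towards change, so the choice is less open than silence alone would suggest. This also stands. Against the change t-test at equal SDs the gain is 12% at r = 0.5 and 4% at r = 0.8. The larger gain of 12–39% over the same r applies only if the 6 h score is the comparator. Still, the same endpoint line also speaks of scoring, and no section defines the quantity.

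Third, the size of the gain, and even its sign, rests on an assumed r and SD ratio. This is correct; the working bounds the loss at about 1.5%.

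A reader might infer from the schedules that the baseline KCCQ is taken after allocation. The documents do not establish this. The columns are weak evidence of order: creatinine is marked under Screening, while section 6.1.2 draws it just before dosing. No text says when the envelope is opened relative to the KCCQ.

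A reader might also conclude that the 6 h-score t-test is the safe choice if the order cannot be guaranteed, because it does not use the baseline. That holds only if knowing the arm shifts the pre-dose score alone. In an open-label trial the 6 h score is also given with the arm known, and if both scores shift, the 6 h-score analysis is the most biased of the three.

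**Conclusion.** The point holds as a minor improvement in precision and specification. The t-test rule covers the KCCQ without a baseline covariate and without a defined quantity. With 20 per arm and equal SDs, ANCOVA narrows the interval by up to 12% against the better t-test, for r between about 0.17 and 0.94. With a pre-dose SD smaller than the 6 h SD it can be wider at some r, but by about 1.5% at most. The sizes rest on assumed correlations, assumed SD ratios, normal data and 20 analysed per arm.

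Two stronger readings are not supported: that the planned test is invalid, and that ANCOVA is narrower whatever the SDs. Scoring of the pre-dose KCCQ after allocation is possible, not established.

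**What to change.** - **Section 8.2, the synopsis and the planned full SAP:** analyse the 6 h KCCQ by ANCOVA with treatment and pre-dose KCCQ, and report the adjusted difference with its 95% CI. Keep one t-test, with the 6 h score or the change named in advance, as a sensitivity analysis.
- **Section 6.1.1 and both schedules:** require the pre-dose KCCQ to be completed before the allocation envelope is opened. This needs to be in place before enrolment.
- **If that order cannot be guaranteed:** report the 6 h-score, change and ANCOVA estimates together and state the limitation, rather than choosing one as free of bias.

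The cost is some wording, one degree of freedom in the KCCQ model, and a fixed order for two steps that already take place. No patients, visits or data are added.

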| | • Furosemide Injection Solution (SCP-101), 8 mg/mL: 80 mg dose administered subcutaneously as 30 mg over the first hour and then as 12.5 mg per hour over the subsequent 4 hours (test treatment) |
| | Since the HFBC gives IV diuretics about 15 times per month, HFBC plans to enroll 40 patients within three to four months. The study requires only one clinical visit – a visit that would have already been scheduled for the patient. |
| NUMBER OF SUBJECTS | The number of subjects in this prospective study is 40. 20 in the IV furosemide group and another 20 in the subcutaneous furosemide group. |
| NUMBER OF SITES | 1 |
| PARTICIPATING COUNTRIES | US |
| SUBJECT POPULATION | Female and male subjects may be enrolled in the study only if all of the inclusion criteria and none of the exclusion criteria are met. |
| | Inclusion Criteria (low risk, intermediate risk): |
| | An Institutional Review Board (IRB) approved informed consent is signed and dated prior to any study-related activities. Male and female subjects ≥ 18 years of age History of at least 3 months treated heart failure (NYHA class II/III/IV), or recent hospitalization for heart failure; presenting to HFBC with decompensated heart failure symptoms including elevated jugular venous pressure, dyspnea and peripheral edema where the decision is made to give IV diuretics Able to participate in the study in the opinion of the investigator Has the ability to understand the requirements of the study and is willing to comply with all study procedures |
| | Exclusion Criteria (high risk): |
| | A subject is not eligible for inclusion if any of the following criteria apply: |
| | • Presenting with symptoms where it is anticipated that there is a high chance of hospitalization such as ischemia, uncontrolled arrhythmia, infection, hemodynamic instability (elevated or low blood pressure), respiratory compromise, or electrolyte |

| | abnormalities (>25% increase in creatinine from baseline, |
|-------------------------|---|
| | potassium, hyponatremia). |
| | • On experimental medication or currently participating in a |
| | cardiovascular research study. |
| | • Presence or need for urinary catheterization, urinary tract |
| | abnormality or disorder interfering with urination |
| | • Any surgical or medical condition which in the opinion of the investigator may interfere with participation in the study or which may affect the outcome of the study |
| | Inability to comply with study requirements |

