6.1.9. Injection Site Inspection

Study staff will inspect the injection site for erythema and edema using the Draize Scale which includes a 5-point scale for erythema and a 5-point scale for edema. (Appendix 3)

In addition to the Draize scale scoring, the investigator will assess the injection site area for other local reactions, including hematomas, thrombosis, induration, infection, necrosis, etc. The Investigator will rate the reactions as mild, moderate or severe and make an assessment as to causality.

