8. STATISTICS

8.1. Determination of Sample Size

For this pilot study, the determination of sample size was primarily based on clinical consideration; with the aim to yield meaningful preliminary data.

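### Section 8.2 sends every categorical variable to a chi-square test that ignores order; this matters mainly for the Treatment Satisfaction Survey, if it is rated in ordered categories

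*Combined protocol and SAP*

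**What the plan says.** Section 8.2 (repeated in the Synopsis) sorts variables into two kinds. Continuous variables get an unpaired two-sided t-test. For the rest, "Differences between treatment groups for the categorical variables will be analyzed using the chi-square test". The significance level is 5%. The section also promises a full analysis plan, which is not among the documents.

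Section 3.1.1 lists, as the third secondary endpoint, "Overall Satisfaction with Treatment- (Treatment Satisfaction Survey". Section 6.1.1 adds only that the survey is given at 6 hours. The number of items, the response levels and the scoring are not stated.

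Section 6.1.9 has the injection site scored "using the Draize Scale which includes a 5-point scale for erythema and a 5-point scale for edema", and has other local reactions graded mild, moderate or severe. Section 7.3 uses the same three grades for adverse events, and 6.1.8 has pain rated 0 to 10. Section 8.3 then says: "Pain assessments and local injection site reactions will be tabulated and assessed using descriptive statistical analysis". Adverse events are likewise to be summarised descriptively. Section 8.3 does not mention satisfaction.

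The planned size is "20 in the IV furosemide group and another 20 in the subcutaneous furosemide group", and in 8.1 "the determination of sample size was primarily based on clinical consideration".

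**The concern.** A Pearson chi-square on a table of two arms by k levels spends k − 1 degrees of freedom on any difference in pattern. It gives the same answer however the levels are shuffled. If one arm is simply more satisfied than the other, the difference runs along the order, and a test that uses the order puts its power there.

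Satisfaction with subcutaneous versus intravenous treatment is part of the secondary objective, and 8.2 is the only rule that applies to it. With 20 patients per arm there is little power to spare. A real shift could be reported as not significant when the same data, ranked, would have shown it. The treatment is open label (5.5), so a change of test after the results are seen would be open to challenge; the test should be fixed beforehand.

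**Working it through.** **No figure to reproduce.** The documents give no power, effect size or category distribution for any outcome. The distributions and odds ratios below are assumptions, shown as a range.

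**Which ratings does 8.2 reach?**

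| Rating | Levels | Where analysed |
|---|---|---|
| Treatment satisfaction | not given | 8.2 only: chi-square if categorical, t-test if a numeric score |
| Draize erythema, Draize edema | 5 each (0–4) | 8.3: descriptive |
| Local reaction severity | 3 | 8.3: descriptive |
| Adverse event severity | 3 | 8.3: descriptive |
| Pain | 11 (0–10) | 8.3: descriptive |

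Only satisfaction has no other home.

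**Inputs.** 20 per arm (Synopsis, number of subjects); two-sided 5% (8.2; two-sidedness is stated there for the t-test and used here for the rank test). Assumed: a five-level item with control probabilities 5/10/20/35/30%, and a proportional-odds shift upwards in the other arm.

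**Shift.** For each cut j: odds of Y ≤ j in the shifted arm = (odds of Y ≤ j in control) / OR. Example at OR 3: control P(Y ≤ 4) = 0.70, odds 0.70/0.30 = 2.333; 2.333/3 = 0.778; P = 0.778/1.778 = 0.4375. The top category therefore goes from 30% to 56%.

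**Sparseness.** With no difference, expected counts per arm are 20 × (0.05, 0.10, 0.20, 0.35, 0.30) = 1, 2, 4, 7, 6. Three of the five columns, or 6 of 10 cells, are below 5.

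**Tests.** Chi-square = Σ(O − E)²/E over non-empty columns, with degrees of freedom equal to the number of non-empty columns − 1. Rank-sum: z = (W − n(2n + 1)/2)/√V with n = 20, where V = (n²/12)[(2n + 1) − Σ(t³ − t)/(2n(2n − 1))] and t is each column total. There were 20,000 simulated trials per setting, so the simulation error is at most √(0.25/20,000) = 0.35 points.

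**Power (%), five levels, satisfaction distribution above:**

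| OR | Chi-square | Rank-sum | Loss |
|---|---|---|---|
| 2 | 10.2 | 22.2 | 12.0 |
| 3 | 23.3 | 44.5 | 21.2 |
| 4 | 36.4 | 62.2 | 25.8 |
| 5 | 48.2 | 74.1 | 25.9 |
| 6 | 57.4 | 82.5 | 25.1 |
| 8 | 70.9 | 90.3 | 19.4 |

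At OR 1 the rejection rates are 3.8% and 4.9%, so the rank test's gain is not bought with false positives. Over five different five-level control distributions the loss is about 10 to 12 points at OR 2, 21 to 27 at OR 3 to 6, and 15 to 19 at OR 8.

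**Power (%), three levels, one third each in control:**

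| OR | Chi-square | Rank-sum | Loss |
|---|---|---|---|
| 2 | 16.0 | 20.6 | 4.6 |
| 3 | 34.7 | 44.0 | 9.3 |
| 4 | 50.8 | 61.4 | 10.6 |
| 6 | 71.7 | 80.8 | 9.1 |

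A skewed three-level distribution peaks at 11.1 points (OR 4).

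**Other formats, OR 2 to 8.** Four levels: about 8 to 20 points. Seven levels: about 14 to 35. Binary: zero (20% against 60% gives 74.8% power with either test). For one assumed non-monotone difference the ranking reverses: chi-square 52%, rank-sum 6%.

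**The case against.** The strongest objection is that 8.3 already deals with most of the ordered ratings. A specific safety section normally governs over a general sentence, and under 8.3 the Draize, severity and pain ratings are tabulated and not tested. This stands. A reader might infer that the plan gives up 20 or more points of power on all its multi-level ratings; the documents do not support that, since no power is lost on an outcome that is not tested. An objective worded as one route versus another does not by itself require a p-value for each safety rating in a pilot. What remains for those ratings is that 8.2 is worded without limit and 8.3 does not say that it overrides it.

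Second, the survey's scale is unknown. If it yields a numeric score, 8.2 sends it to the t-test. A linear trend test on the category scores, a close analogue, has 41.5% power at OR 3 in the setting above, against 44.5% for the rank-sum, so little would be lost. If the items are yes/no, nothing is lost. This also stands, and makes the point conditional.

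Third, this is a pilot of 40 patients with no power claim, and a full analysis plan is promised. That limits the stakes but does not close the gap: 8.2 already names the test, and the later plan is not here to correct it. As for non-monotone differences, where chi-square is stronger, whether one route is more satisfactory than the other is a directional question.

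**Conclusion.** The point holds in a limited form. The plan's only categorical test ignores order, and no ordinal test is named. The exposed outcome is treatment satisfaction, if it is rated in three or more ordered categories. The Draize and severity ratings join it only if 8.2 is taken to cover them despite 8.3.

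Under a proportional-odds shift at 20 per arm, a five-level item loses about 11 points at OR 2 and about 21 to 26 points at OR 3 to 6; three levels lose about 5 to 11 and a binary item nothing. These figures rest on assumed distributions, level counts and effect sizes, so no single figure can be attached to the trial.

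Nor should a reader infer that chi-square gives too many false positives here: in the five-level satisfaction setting it rejects 3.8% of the time with no difference. The fault is lost sensitivity. The primary endpoints, urine volume and natriuresis, are continuous and untouched.

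**What to change.** In 8.2, and in the matching Synopsis text, add: *Ordered categorical outcomes compared between arms, including satisfaction items rated in ordered categories, will be compared with the Wilcoxon rank-sum test with tie correction; chi-square is kept for unordered and binary variables.*

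In 8.3, add: *Draize, reaction severity and pain ratings remain descriptive; if any is compared between arms, the rank-test rule of 8.2 applies, with one value per patient and none as the lowest level.* The last clause is needed because a severity grade exists only for patients who have a reaction, and a patient may have several.

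State the survey's items, response levels and scoring, since these decide which test applies.

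The cost is two sentences and a description of a form that the site must have in any case. No further data or patients are needed.
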